2.2. Treatment Period

2.2.1. Part A (Phase 1; dose escalation)

2.2.1.1. Pre-screening

Subjects with advanced-stage, relapsed and/or refractory solid tumors (subjects must have received an anti-PD-1/PD-L1 treatment [alone or in combination] and progressed on or relapsed after completion of anti-PD-1/PD-L1 treatment) with no available approved therapeutic alternative will sign a Pre-screening Informed Consent form (ICF) allowing the site/Sponsor to evaluate serum GDF-15 levels prior to entering the screening period.

2.2.1.2. Screening

For Part A (Phase 1; dose escalation) only, based on pre-screening GDF-15 serum levels, the Sponsor will approve pre-screened subjects for consent on the main study. Ideally 50% of enrolled subjects per dose level should show increased serum GDF-15 levels at pre-screening (> 1.5 ng/ml).

Subjects considered to be eligible to participate in the study will sign an ICF allowing the site/Sponsor to perform the screening procedures to confirm eligibility for the study (therefore, Screening is defined as the day of informed consent, and “Screening” is used throughout the synopsis and protocol to refer to this visit). The Screening Period is up to 21 days (for Part A) and up to 28 days (for Part B).

2.2.1.3. Part A (Phase 1; dose escalation)

This study will employ a standard “3+3” dose escalation design for which 3 to 6 subjects will be enrolled at each assigned dose level, per cohort, depending on the occurrence of DLTs.

The planned doses of CTL-002 to be tested are outlined below:

- Cohort 1: 0.3 mg/kg
- Cohort 2: 1.0 mg/kg
- Cohort 3: 3.0 mg/kg
- Cohort 4: 10 mg/kg
- Cohort 5: 20 mg/kg

The start dose of 0.3 mg/kg for Cohort 1 is fixed. Doses explored in Cohorts 2-5 (as outlined above) may be modified by the SRC established for the study based on emerging data (i.e., available safety, PK/pharmacodynamic, other biomarker data).

The DLT Observation Period will be the first 2 treatment cycles (i.e., first 4 weeks) for each dosing cohort. All treatment cycles are defined as 2 weeks in duration. CTL-002 will be administered Q2wk as an IV infusion over 60 minutes. Subjects will first receive one dose of CTL-002 given as monotherapy for one cycle, followed by a combination of CTL-002 given together with the defined anti-PD-1 checkpoint inhibitor for one cycle, where the defined checkpoint inhibitor will be administered at a dose of 240 mg IV given once every 2 weeks infused over approximately 30 minutes.

For the combination, CTL-002 and the defined checkpoint inhibitor will be given on the same day concomitantly, where CTL-002 will always be administered first and for the first combination infusion, there will be a 30-minute observation period to assess safety, which will then be followed by the defined checkpoint inhibitor infusion administered per SmPC or Product Label and local guidelines. The period of observation may be modified (i.e., shortened or lengthened) based on emerging safety data.

The first 2 treatment cycles (i.e., first 4 weeks) represent the DLT Observation Period. Thereafter, subjects will continue with the combination treatment, until progression or until withdrawal from the study for any other reasons (e.g., toxicity or subject withdraws consent).

Additional, intermediate dose cohorts may be explored based on emerging data and upon SRC request. The maximum dose of CTL-002 to be tested in this study will not exceed 20 mg/kg.

All subjects will be hospitalized overnight after receiving the first dose of CTL-002 and also after receiving the first combination dose of CTL-002 and the defined checkpoint inhibitor, for the purposes of safety observation and to enable logistical collection of sampling time-points (e.g., PK).

Dose Escalation Rules:

Initially, 3 subjects will be enrolled in any given dose cohort.

- If 0/3 subjects experience a DLT, then proceed to next dose
- If 1/3 subjects experience a DLT, then an additional 3 subjects will be tested at the same dose level
- If $\geq 2/3$ subjects experience a DLT, this is considered the limiting dose and then an additional 3 subjects will be tested at the previous dose level to ensure a total of 6 subjects treated safely at that dose. In the situation where there is no lower dose level (i.e., if limiting dose is confirmed in Cohort 1), the Sponsor/SRC will make a recommendation about study continuation
- If 1/6 subjects experience a DLT, then proceed to the next dose level
- If $\geq 2/6$ subjects experience a DLT, this would be defined as the limiting dose and dose escalation will stop. The previous lower dose would be considered the MTD. At least 6 subjects evaluable for safety must be enrolled at this dose level before it may be confirmed as the MTD
- Intermediate dose levels may be explored based on emerging data (safety, PK/pharmacodynamic) and if explored, will be discussed and agreed by the SRC and such decisions will be documented in writing

Note: Moving from 1 dose cohort to the next requires subjects eligible for evaluation. Evaluable subjects must have received 2 weeks of CTL-002 monotherapy and 2 weeks of the combination (i.e., a subject must complete the 4-week DLT Observation Period). Subjects who have confirmed disease progression during the 4-week DLT Period or those subjects who discontinue for any reason, other than a DLT, may be replaced in the applicable dosing cohort. Subjects who experience a DLT will not be replaced.

In each dose cohort, the first subject will be dosed and observed for 6 calendar days to allow for initial assessment of safety before any other subjects may be dosed. Upon confirmation that the

first subject has tolerated CTL-002 monotherapy and there are no significant toxicities that preclude further dosing, the second subject may be dosed and this subject will be observed for safety for 2 days. Upon confirmation that the second subject has tolerated CTL-002 monotherapy and there are no significant toxicities within the first 2 days that preclude further dosing, the third subject may be dosed.

In the case a DLT is observed in the first 3 subjects, there will be a 2-day stagger between the enrolment of the 3 additional subjects.

The first subject in the next higher dose cohort will not receive treatment with CTL-002 until the previous dose cohort has met the criteria for dose escalation and agreement from the SRC has been obtained and the decision documented in writing.

Intra-Patient Dose Escalation in Extended Treatment

If any Cohort 1 subjects are still on 0.3 mg/kg treatment when Cohort 2 has been completed and reviewed by the SRC, the subjects can be increased to the Cohort 2 dose of 1.0 mg/kg.

If any Cohort 1 or 2 subjects are still on 1.0 mg/kg treatment when Cohort 3 has been completed and reviewed by the SRC, the subjects can be increased to the Cohort 3 dose of 3.0 mg/kg.

Note: Any subjects still on 0.3 mg/kg treatment must be treated at 1.0 mg/kg prior to advancing to 3.0 mg/kg in agreement with the Sponsor Medical Monitor.

The maximum a subject dose can be increased to, through intra-dose escalation, will be 3.0 mg/kg.

Available safety, PK/pharmacodynamic data, as well as preliminary efficacy data will inform the MTD/dose(s) to be further explored in Part B of the study.

The MTD is defined as the highest dose level of CTL-002 at which no more than 1 out of 6 subjects experienced a DLT during the first 2 treatment cycles (i.e., the first 4 weeks, where CTL-002 is given as monotherapy [Weeks 1 and 2] and in combination with the defined checkpoint inhibitor [Weeks 3 and 4]).

In addition, for Cohorts 3-5, in the absence of any DLT, an additional 3 subjects can be recruited into each of these cohorts (up to a total of 6 subjects per cohort), to increase the understanding of the PK and pharmacodynamic data. This occurs while dose escalation continues. These additional “backfill” subjects will receive the combination treatment of CTL-002 and the defined checkpoint inhibitor once every 2 weeks from Cycle 1 Day 1 onwards, with CTL-002 always administered first and the defined checkpoint inhibitor given thereafter as outlined above.

For Part A subjects (except backfill subjects), 3 sequential tumor biopsies are mandated; one biopsy at baseline, the second biopsy prior to the initiation of the combination therapy (after 2 weeks) and the third after the first cycle of combination therapy (either at the End of Treatment visit or, if combination treatment is continued, at the end of Cycle 2/beginning of Cycle 3).

For backfill subjects, only 2 biopsies are mandated; one at baseline, and the second after 4 weeks of combination treatment (either at the End of Treatment Visit or, if combination treatment is continued, at the end of Cycle 2/beginning of Cycle 3).

These biopsies are mandatory in order to assess immune cell infiltration in the tumor. If a biopsy cannot be taken for safety reasons, this must be discussed with the Medical Monitor.

Dose-Limiting Toxicity Criteria

The DLT Observation Period is the first 2 treatment cycles (i.e., 4 weeks). The SRC will review all DLTs as per the SRC charter. A DLT is defined as any of the following AEs graded using the NCI-CTCAE Version 5.0.

Hematologic Toxicity:

- Any Grade 4 hematologic toxicity

Non-Hematologic Toxicity:

- Any Grade 4 non-hematologic toxicity
- Any other \geq Grade 3 non-hematologic toxicity lasting more than 96 hours despite appropriate supportive therapy
- Any \geq Grade 3 pneumonitis, adrenal insufficiency, myocarditis, hepatitis (immune-related \geq Grade 3 aspartate aminotransferase [AST], alanine aminotransferase [ALT] and total bilirubin elevation)
- Occurrence of Stevens-Johnson syndrome (SJS)

General Toxicity:

- Any Grade 5 toxicity
- Any other toxicity that is not captured with above regulations but is considered by the Investigator and the SRC as qualifying for a dose-limiting event/toxicity (e.g., any permanent discontinuation criteria of the defined anti-PD-1 checkpoint inhibitor)

Note: Transfusions of blood products or use of growth factors are **NOT** permitted during the Screening Period or during the 4-week DLT Observation Period (with the exception of a requirement to treat a DLT/SAE).

2.2.1.4. Maximum Tolerated Dose

The MTD is defined as the highest dose level of CTL-002 at which no more than 1 of 6 subjects experienced a DLT during the first 4 weeks of treatment (2 treatment cycles, DLT Period). The MTD is effectively considered to be the highest dose associated with a DLT in the first 4 weeks of treatment in $<33\%$ of subjects.

2.2.2. Part B (Phase 2a; expansion)

In Part B (Phase 2a) of the study, various cohorts with defined tumor indications as provided above will be enrolled.

The treatment dose for CTL-002 in Part B is set at 10 mg/kg Q2wk or 20 mg/kg Q3wk.

Pharmaco-modelling and obtained PK/pharmacodynamic data from Part A indicate complete GDF-15 neutralization at the dose of 10 mg/kg and the dosing interval Q2wk or the dose of 20 mg/kg and the dosing interval Q3wk or Q4wk in serum and tumor vasculature (tumor microenvironment) in subjects with a wide range of baseline GDF-15 serum levels. In the current development phase (Phase 2a) the dosing interval follows for subject convenience the dosing interval of the checkpoint inhibitor. No safety events of concern and no DLT have been observed

at any dose in Phase 1, including the doses of 10 mg/kg and 20 mg/kg. In addition, the for this initial Phase 2 exploration selected dose of 10 mg/kg and 20 mg/kg (with dosing interval of Q2wk and Q3wk, respectively) provide exposure that is still below the no-observed adverse effect level (NOAEL) in non-human primate (NHP).

Depending on further PK/pharmacodynamics data observed and safety and efficacy data, the SRC may modify these Phase 2 doses if seen as recommended or if a second dose is decided to be explored (all via substantial amendment).

In the expansion cohorts, subjects with advanced-stage, relapsed/refractory solid tumors in non-curable state that have either of the following indications will receive treatment with a combination of CTL-002 and the defined checkpoint inhibitor

(1) bladder cancer, hepatocellular cancer, non-small cell lung cancer, cutaneous squamous-cell carcinoma or melanoma (for melanoma, only cutaneous and mucosal forms, not uveal/ocular) (approved anti-PD-1/PD-L1 indications) that relapsed on or were primary refractory to prior anti-PD-1/PD-L1 therapy with an approved anti-PD-1/PD-L1 compound or

(2) colorectal cancer (MSS/mismatch-repair competent) and have not received any prior anti-PD-1/PD-L1 therapy, or

(3) biomarker cohort with mixed solid tumors (“basket” cohort) that are relapsed on or were primary refractory to prior anti-PD-1/PD-L1 therapy with an approved anti-PD-1/PD-L1 compound and that have exhausted existing treatment options or are not eligible for them anymore.

- For the **first group** (currently approved anti-PD-1/PD-L1 indications) N = 14 response-evaluable subjects each will be recruited for bladder cancer, hepatocellular cancer, non-small cell lung cancer, and melanoma, for cutaneous squamous-cell carcinoma N = 12.
- For the **second group** (currently non-approved anti-PD-1/PD-L1 indication) N = 10 response-evaluable subject will be recruited for colorectal cancer (MSS/mismatch-repair competent).
- The **third group** (biomarker cohort with mixed solid tumors; “basket” cohort) investigated, are subjects with anti-PD-1/PD-L1 relapsed/refractory mixed advanced solid tumors. Up to N = 75 subjects are planned to be enrolled to have at least N = 25 response-evaluable with TPS PD-L1 > 1 status and ideally up to N = 50 response-evaluable subjects with PD-L1 TPS ≤ 1. If recruitment of 25 response-evaluable subjects with TPS PD-L1 > 1 is achieved, recruitment into the third group will be stopped and the TPS ≤ 1 cohort will be evaluated with given patient number in descriptive way.

For **all groups** the following additional requirements and restrictions apply:

- (a) **All subjects generally must have received a currently for their tumor type approved anti-PD-1/PD-L1 compound**; non-approved, experimental anti-PD-1/PD-L1 treatments are not permissive for enrolment into this group (does not apply for other cohorts) unless condition (e) applies. (Group 2 with MSS-CRC is exempted from this regulation)
- (b) **Baseline tumor biopsies are mandatory for all subjects** to further evaluate for predictive biomarkers of response as detected in Phase 1 and to further deepen the understanding of “cold-to-hot” tumor transitions for response under treatment.
- (c) For **melanoma, cutaneous squamous-cell carcinoma** and the **biomarker cohort with mixed solid tumors** (“basket” cohort), an additional **follow-up, on-treatment biopsy** is

mandatory to assess for immunologic changes in the tumor. **Important note:** All biopsies are only taken if considered **safe** and **feasible** by the treating physician/Investigator.

- (d) All subjects that **achieve/maintain stable disease by week 24** but do not show tumor shrinkage beyond – 10% as per RECIST criteria can undergo if desired by the treating physician and agreed by the patient stereotactic radiotherapy of one or more tumor lesions to increase neoantigen exposure and potential for response improvement (as was seen in two Phase 1 patients). This should always be pre-discussed with the medical representative of the sponsor and the radiotherapy area should not include all lesions that are used for RECIST response assessment to allow for abscopal antitumor effect assessment. **Note:** In case of initiation of stereotactic radiotherapy in addition to study treatment, an optional tumor biopsy should be performed no earlier than 4 weeks after initiation of radiotherapy, if seen as safe and medically feasible by the treating physician.

For the **third group** (biomarker cohort with mixed solid tumors; “basket” cohort) the following additional requirements and restrictions apply:

- (f) Up to **5 subjects** (but no more) in the PD-L1 TPS > 1 group with **tumor indications that are currently not yet approved at all for anti-PD-1/PD-L1 treatment** may be enrolled if treated with a currently approved anti-PD-1/PD-L1 (for other indication(s)), if also all other criteria for the group apply. For the PD-L1 TPS ≤ 1 group this may be up to 10 patients.
- (g) No subjects with melanoma (cutaneous, mucosal or uveal) can be enrolled into this cohort.

Treatment cycles are as follows:

- Q2wk for bladder cancer, hepatocellular cancer, non-small cell lung cancer, melanoma, colorectal cancer and biomarker cohort with mixed solid tumors (“basket” cohort)
 - 10 mg/kg CTL-002 as an IV infusion over approximately 60 minutes, Q2wk
 - 240 mg nivolumab as an IV infusion over approximately 30 minutes, Q2wk
- Q3wk for the cutaneous squamous-cell carcinoma cohort
 - 20 mg/kg CTL-002 as an IV infusion over approximately 60 minutes, Q3wk
 - 350 mg cemiplimab as an IV infusion over approximately 30 minutes, Q3wk

In all subjects of all cohorts a baseline biopsy is mandatory to evaluate for potential predictive biomarkers (either fresh biopsy or archived biopsy taken within 120 days prior to treatment start). For melanoma, cutaneous squamous-cell carcinoma and the biomarker cohort with mixed solid tumors (“basket” cohort), an additional on-treatment biopsy is mandatory. If there is a safety risk at the discretion of the investigator to perform an on-treatment biopsy, this must be discussed with the Medical Monitor. An optional third biopsy can be taken at the next medically feasible timepoint during ongoing treatment in case the first biopsy is evaluable, but the second biopsy is non-evaluable, to assure assessable histology data.

In cutaneous squamous-cell carcinoma, multiple punch biopsies will be taken at a single timepoint (as per clinical possibility, ideally 3-5), as extensive molecular analyses are pursued (messenger ribonucleic acid [mRNA] expression analyses, such as T cell clonality analyses, RNAseq, nanostring analyses or genome sequencing etc.).

Enrolment into the Phase 2a cohorts may occur in parallel. Subjects that do not reach the first response assessment for reasons other than disease progression will be replaced to assure a full set of response assessable subjects. All subjects will be treated until progression under observation of RECIST criteria.

For the purposes of safety observation and to enable logistical collection of sampling time points (i.e., PK sampling), all subjects will be hospitalized overnight after receiving the first dose of CTL-002 (in case of future monotherapy cohort) or after receiving the first combination dose with CTL-002 and the defined checkpoint inhibitor (combination therapy cohort), respectively.

As part of Phase 2a, a dedicated CTL-002 monotherapy cohort may be conducted within a defined tumor indication to explore the safety profile of CTL-002 given as monotherapy (e.g., in subjects with advanced-stage melanoma) at a later timepoint, introduced per substantial amendment.

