- For the **first group**, for bladder cancer, hepatocellular cancer, non-small cell lung cancer, and melanoma, a minimum of 1 responder each is required to allow for continuation. Treating an additional N = 13 subjects shall generate a total of ≥ 4 responders to assume the overall response rate to be 20% or higher. For cutaneous squamous-cell carcinoma, a minimum of 2 responders is required to allow for continuation. Treating an additional N = 24 subjects shall result in a total of ≥ 6 responders to assume the overall response rate to be 25% or higher
- For the **second group**, for colorectal cancer with N = 10 fixed for the first stage, if at least 1 responder was observed in the first stage, an additional N = 19 subjects may be added to a cohort. In a total of N = 29 subjects at least ≥ 4 responders are expected to assume the true response rate could be at 20% or higher
- For the **third group** (biomarker cohort with mixed solid tumors; “basket” cohort) with up to N = 75 subjects no such further expansion is considered. Instead, depending on response rate, - depth and - duration observed a potential registration size trial design will be considered and reviewed with the competent authorities (separate protocol). For the PD-L1 TPS > 1 group (“hot” tumors) a response rate of ≥ 30% is seen as clinically of significance, for the PD-L1 TPS ≤ 1 (“cold” tumors) a response rate > 20%.

In case of progressive disease (PD), treatment beyond progression might be applied as per Investigator assessment in agreement with the patient.

Proposed indications were selected based upon an **extensive translational research program** by the Sponsor, indicating a negative impact of GDF-15 on the immune response in the tumor microenvironment in the proposed indications, resulting in lack of immune cell infiltration, activation and in some indications proven resistance to checkpoint inhibitor treatment. In all subjects of all cohorts a baseline biopsy is mandatory to evaluate for potential predictive biomarker. In selected cohorts (i.e., melanoma, cutaneous squamous-cell carcinoma and in the

biomarker cohort with mixed solid tumors [“basket” cohort]) sequential, dual tumor biopsies will be taken in subjects with accessible lesions. Enrolment into all cohorts may occur in parallel.

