3.5. Replacement of Subjects

Subjects that are withdrawn from the study but are evaluable for safety will not be replaced. Any subject that is withdrawn and is not considered evaluable for safety during the Part A (Phase 1; dose escalation), will be replaced to ensure a minimum number of evaluable subjects.

Evaluable subjects for Part A (Phase 1; dose escalation) must have received the first 2 treatment cycles (i.e., a subject must complete the 4-week DLT Observation Period consisting of 2 weeks CTL-002 monotherapy and 2 weeks combination therapy or Part A backfill subjects must have completed the first 4 weeks of combination treatment). Subjects who have confirmed disease progression during the 4-week DLT Period or those subjects who discontinue for any reason, other than a DLT, may be replaced in the applicable dosing cohort. Subjects who experience a DLT will not be replaced.

Evaluable subjects for Part B (Phase 2a; expansion) must have received the first 4 treatment cycles (in case of combination treatment with nivolumab) or 3 treatment cycles (in case of combination treatment with cemiplimab), (i.e., 8 or 9-weeks combination therapy in any combination therapy cohorts), except if they have confirmed disease progression during these 4 or 3 in case of cemiplimab) cycles or discontinue for toxicity. Subjects discontinued for other reasons may be replaced in the applicable dosing cohort.

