8.1. Statistical Methods

This study is explorative in nature. Thus, no formal statistical comparisons are planned. Descriptive and inferential statistics will be used to summarize the data. Continuous variables will be summarized by number, mean, standard deviation, median, minimum and maximum values. Categorical variables will be summarized by subject counts and related percentages.

Percentages will be calculated using the total subjects per dose group (Part A), and cohort (Part B).

As a general principle, all summaries from Part A, presented by dose group and Part B, presented by cohort, will be displayed separately. No pooling of data from the two parts is planned.

In Part B (Phase 2a; expansion), cohorts with several defined tumor indications will be treated to detect efficacy signals, in a screening effort to identify tumor indications where CTL-002 has clinically relevant antitumor activity. All indications have been selected based upon translational research results by the sponsor and other scientific groups that indicate an immunosuppressive role of GDF-15 in these tumor indications.

To achieve this and based upon a **conditional probability calculation** the following subject numbers are recruited:

- For the **first group**, for bladder cancer, hepatocellular cancer, non-small cell lung cancer, and melanoma, N = 14 response-evaluable subjects will be initially recruited per each tumor indication. This shall allow to detect 2 responses in a cohort with 80% probability if the true response rate is 20% or more, and at least 1 response in the cohort with 77% probability if the true response rate is 10% or more. For cutaneous squamous-cell carcinoma, N = 12 response-evaluable subjects will be recruited initially. This should result in 2 responses or more with 80% probability if the true response rate is 25% or higher
- For the **second group** (colorectal cancer [MSS/mismatch-repair competent, a currently non-approved anti-PD-1/PD-L1 indication]), N = 10 response-evaluable subject will be recruited. This shall allow to detect 1 response with 89% probability (if the true response rate is 20% or more), and 1 response with 80% probability if the true response rate is 15% or more

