8.2. Subject Selection for Analyses

The statistical analysis will be conducted in the following data sets:

- The Safety Analysis Set will consist of all subjects who received at least one dose of CTL-002. Subjects will be analyzed according to the dose level initially received
- The PK Analysis Set will consist of all subjects who received at least one dose of study medication and have at least one measurable concentration of CTL-002
- The Efficacy Evaluable Analysis Set as per statistical definition will consist of all subjects who complete at least 2 cycles of treatment (e.g., 1 cycle monotherapy followed by 1 cycle combination therapy for Part A or 2 cycles combination therapy for Part A backfill and Part B subjects), and have baseline and at least one valid post-baseline tumor assessment demonstrating progression or were declared to be clinically progressing or terminated treatment due to a treatment-related AE

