8.3.3. Efficacy Analysis

Efficacy analyses will be based on the Efficacy Evaluable Analysis Set and will include summaries of confirmed PR/CR, ORR, DoR, PFS, TTR, and OS by dose level (Part A) or cohort (Part B). Tumor response will be evaluated according to institutional standards using RECIST V1.1 for solid tumors, as well as iRECIST criteria. The definitions of the response evaluation endpoints are as follows:

Table 10 Definitions of Response Evaluation (RECIST V1.1)

Duration of Response:	Duration of response will be measured from the time that measurement criteria are met for CR or PR (whichever status is recorded first) until the first date that PD or death is documented. This analysis will include subjects with overall best response being CR or PR only. Subjects who neither progressed nor died will be censored at the date of the last tumor assessment
Overall Response Rate	Overall response rate is defined as the percentage of subjects with a CR or PR as assessed by RECIST V1.1. A responder is defined as a subject experiencing either a CR or PR by these criteria. Subjects with no tumor assessment after the start of study treatment are to be considered as non-responders.
Progression Free Survival	Progression-free survival is defined as the length of time between first study drug administration and the date of the first occurrence of disease progression or death from any cause.
Time to Response	Time to response will be measured from the time of first study administration until the day of documented CR or PR (whichever status is recorded first). Subjects without response will be censored at the date of the last tumor assessment or the date of death.
Overall Survival	Overall survival is defined as the time from the study drug administration to the date of death, regardless of the cause of death. Subjects who were alive at the time of the analysis will be censored at the date the subject was last known to be alive. Subjects without follow-up assessment will be censored at the day of their last dose and subjects with no post-baseline information will be censored at the time of their first study drug administration.

Abbreviations: CR = complete response; PD = progressive disease; PR = partial response; RECIST = Response Evaluation Criteria in Solid Tumors

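### Section 2.2.2 and the synopsis replace Part B subjects who stop for toxicity before the first scan, Section 3.5 keeps them as evaluable, and nothing says which rule governs the cohort counts

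*Protocol*

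**What the plan says.** **Replacement, first rule.** Section 2.2.2, and the same sentence in the synopsis: "Subjects that do not reach the first response assessment for reasons other than disease progression will be replaced". Replacement is mandatory and progression is the only exception. It need not be confirmed.

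**Replacement, second rule.** Section 3.5 requires 4 cycles (nivolumab) or 3 cycles (cemiplimab) for a Part B subject to be evaluable, "except if they have confirmed disease progression during these 4 or 3 in case of cemiplimab) cycles or discontinue for toxicity". It continues: "Subjects discontinued for other reasons may be replaced in the applicable dosing cohort". The section opens with a general statement: "Subjects that are withdrawn from the study but are evaluable for safety will not be replaced".

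**Analysis.** Section 8.2 builds the Efficacy Evaluable Analysis Set from subjects who completed at least 2 cycles and have valid baseline and post-baseline assessments, "or were declared to be clinically progressing or terminated treatment due to a treatment-related AE". Table 10 in Section 8.3.3 says of ORR: "Subjects with no tumor assessment after the start of study treatment are to be considered as non-responders". Appendix 1, A 1.6, asks that every included subject be given a response category, and lists early death from malignant disease, from toxicity and from other causes.

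**Where the count is used.** Stage 1 needs 14 response-evaluable subjects (bladder, hepatocellular, lung, melanoma), 12 (cutaneous squamous-cell) or 10 (colorectal). For the cohorts of 14, "a minimum of 1 responder each is required to allow for continuation". Section 8.1 then sets the bars at 4/27, 6/36 and 4/29.

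**The concern.** A toxicity stop before the week 8–9 scan has opposite consequences under the two rules: replaced under Section 2.2.2, kept under Section 3.5. A death without progression, or a loss to follow-up, must be replaced under one and may be replaced under the other. Clinical progression, or an early death from disease, is exempt under Section 2.2.2. Under Section 3.5 its status is unclear when no confirming scan exists.

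This matters because the binomial figures behind the cohort sizes treat each counted place as having the same response probability. Early toxicity and early death are outcomes of treatment. If those subjects leave the count and new ones take their places, the counted response rate exceeds the rate among everyone treated, and the bars are easier to reach than their stated operating characteristics imply. With bars of 1 or 2 responders in 10 to 14 subjects, a few exchanged places can matter. The replacement rule also acts during accrual, so an analysis plan written later cannot fully undo it.

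**Working it through.** **1. The two rules side by side (Part B, before the first scan)**

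| Reason for leaving | Section 2.2.2 and synopsis | Section 3.5 |
|---|---|---|
| Confirmed progression | not replaced | evaluable |
| Clinical progression, no confirming scan | not replaced | unclear |
| Toxicity | replaced | evaluable |
| Death without progression | replaced | not addressed by name; may be replaced if an other reason |
| Other loss | replaced | may be replaced |

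**2. The plan's own figures reproduce**

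Exact binomial tail for 14 subjects at p = 0.20: P(X ≥ 2) = 0.802. The plan says: "This shall allow to detect 2 responses in a cohort with 80% probability if the true response rate is 20% or more".

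Two-stage probability, with n1, n2 the stage sizes, r1 the continuation bar and r the final bar:

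P(pass) = Σ over x from r1 to n1 of P(X1 = x) · P(X2 ≥ r − x)

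- 14 + 13, at least 1 then at least 4, p = 0.20: 0.807
- 12 + 24, at least 2 then at least 6, p = 0.25: 0.803
- 10 + 19, at least 1 then at least 4, p = 0.20: 0.801

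All three match the stated 80% power.

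**3. Effect of replacement**

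Let p be the response rate among all treated subjects and d the share who leave unscanned without response and are replaced. The rate among counted subjects is q = p / (1 − d).

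Inputs not in the documents:
- d is not given. The range used is 4% to 25%. The low end is the Part A figure of 24 evaluable out of 25 treated (1/25 = 4%; Sections 1.7.1 and 1.8). Part A evaluability was defined over 4 weeks, not 8–9.
- No null rate is stated for the Simon cohorts. A background of 5–10% appears in Section 8.1 only for the basket group with TPS > 1; using it here is an assumption.

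Probability of passing 4/27 (at least 1 of 14, then at least 4 of 27):

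| d | q at p = 5% | pass | q at p = 10% | pass |
|---|---|---|---|---|
| 0 | 5.0% | 4.2% | 10.0% | 27.4% |
| 4% | 5.2% | 4.8% | 10.4% | 30.0% |
| 10% | 5.6% | 5.8% | 11.1% | 34.3% |
| 15% | 5.9% | 6.9% | 11.8% | 38.5% |
| 25% | 6.7% | 9.9% | 13.3% | 48.3% |

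The other cohorts move the same way. At p = 10% and d = 15%, colorectal (4/29) goes from 28.9% to 39.9% and cutaneous squamous-cell (6/36) from 10.6% to 18.1%.

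On the reported rate: at d = 10%, filling 27 places takes 27 / 0.90 = 30 treated subjects, so 4 responders read as 4/27 = 14.8% instead of 4/30 = 13.3%.

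**4. Do the analysis sections repair it?**

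Table 10 and A 1.6 point to counting these subjects as non-responders. But efficacy is analysed on the Efficacy Evaluable set, which requires 2 completed cycles, so a subject who stops in cycle 1 is outside it. A subject who stops later for a treatment-related AE is inside that set, yet replaced under Section 2.2.2. The Simon bars are set on response-evaluable places. The repair is partial.

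**The case against.** The strongest reply is that replacement governs recruitment and does not by itself remove anyone from the ORR denominator. Table 10, A 1.6 and the treatment-related-AE route into the efficacy set all keep early failures in view. This stands as mitigation. It leaves the cycle-1 stops and the Simon counts uncovered.

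A reader might infer that both rules discard treatment failures. The text does not support that: Section 2.2.2 exempts progression without requiring confirmation, and Section 3.5 keeps toxicity stops and opens with a no-replacement statement for subjects evaluable for safety. Reading clinical progression as replaceable under Section 3.5 rests on the single word confirmed, so it is an ambiguity and not a stated rule.

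A reader might also take the upper end of the range as expected. Phase 1 reported no DLT and no Grade 4 or 5 treatment-emergent event, which points to a small share. The calculation also counts every replaced subject as a failure. Losses unrelated to disease or treatment would still be replaced under the fix, so the table overstates what the fix alone would change.

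Finally, the study is described as explorative, and expansion is a joint decision of the SRC and Sponsor on activity and safety, not an automatic pass. Nor do the documents leave the choice of rule to individual sites. These points limit the consequence but do not settle which rule applies.

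**Conclusion.** The contradiction is established from the current text without any assumed rate. The certain conflict covers toxicity stops (replaced against kept) and non-progression deaths and losses (mandatory against optional replacement). The treatment of unconfirmed progression under Section 3.5 is unclear. The direction of bias under Section 2.2.2 is also certain: it raises the counted response rate. If Section 3.5 governs, that bias does not arise for toxicity stops.

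The size is conditional. For a replaced share of 4–25%, the chance of passing 4/27 goes from 4.2% to 4.8–9.9% at an all-treated rate of 5%, and from 27.4% to 30.0–48.3% at 10%. The low end is better supported by Phase 1. Both the share and the application of the 5–10% background to these cohorts are assumptions. The point should be corrected, but it does not show that any cohort has passed its bar wrongly.

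**What to change.** Reconcile the synopsis and Sections 2.2.2, 3.5 and 8.2 into one counting rule that agrees with Table 10 and A 1.6:

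- A dosed subject who dies, progresses (radiologically or clinically) or discontinues for toxicity before the first scan counts as a non-responder in the cohort N, the Simon counts and the ORR denominator, and is not replaced.
- Replacement is limited to subjects not dosed, or lost for documented reasons unrelated to disease or treatment.

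This concerns counting only and changes no treatment. Section 1.7.1 reports 55 Part B subjects already treated by 27 October 2022 in an open-label trial, so the rule must not be applied selectively. Apply it to every Part B subject regardless of response, account for those already replaced, and report ORR on all treated subjects alongside.

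The cost is an amendment to four places, a reconciliation of past replacements, and possibly a slightly lower ORR.
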